3.1 Primary Endpoint

3.1.1 Overall response rate (ORR) with the combination of blinatumomab and pembrolizumab in adult subjects with relapsed or refractory B-cell acute lymphoblastic leukemia be defined as the CR rate plus the CRh rate after 1 or 2 cycles of combination therapy. CR is defined as <5% lymphoblast in the bone marrow without evidence of circulating lymphoblasts or extramedullary disease. CRh is defined as for CR except with platelet count >50,000/microliter, hemoglobin >7 g/dL, and ANC >500/microliter. ORR will be compared to historical controls treated with blinatumomab alone.

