Patients achieving a CR/CRh after 2 cycles will complete a total of 5 cycles of blinatumomab and pembrolizumab in the absence of relapse.

Patients not achieving a CR/CRh after 2 cycles of therapy or progressing after Day 15 of Cycle 1 will go off study.

Patients may proceed to allogeneic hematopoietic cell transplantation as consolidation any time after complete remission. Such patients will be censored for survival at time of initiation of conditioning regimen.

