5.1.6 Response assessment

Response will be assessed by bone marrow aspiration and biopsy on:

- Cycle 1, Day 12, 13, or 14
- Cycle 1, Day 29 + 8 days
- Cycle 2, Day 29 + 8 days
- Cycle 3, Day 29 + 8 days
- Cycle 4, Day 29 + 8 days
- Cycle 5, Day 38 + 8 days

Bone marrow aspiration and biopsy should occur at the time of any relapse or suspected relapse.

Bone marrow aspirates and biopsies should be sent for standard morphology, flow cytometry, karyotype, and *in situ* hybridization for any abnormalities documented on screening bone marrow studies.

Minimal residual disease testing on a first pull bone marrow aspirate should be sent overnight to University of Washington for analysis.

Requisition form is available in **Appendix C**.

For patients with extramedullary disease at diagnosis, repeat imaging using the same modality as at diagnosis is to be performed to assess response on:

- Cycle 1, Day 12, 13, or 14
- Cycle 1, Day 29 + 8 days
- Cycle 2, Day 29 + 8 days

Cycle 5, Day 38 + 8 days

Repeat imaging should occur at the time of any relapse or suspected relapse.

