7.1 Assessment of disease response

7.1.1 Definitions

Evaluable for toxicity. All patients will be evaluable for toxicity from the time of their first treatment on study.

Evaluable for objective response. Only those patients who have measurable disease present at baseline who have received at least one cycle of therapy and have had their disease re-evaluated will be considered evaluable for response. These patients will have their response classified according to the definitions stated below.

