10.4 Evaluable Subjects and Subject Replacement

Stage 1 (Safety evaluation)

Evaluable subjects are defined as any patient receiving the combination of blinatumomab and pembrolizumab starting day 15 of Cycle 1. The DLT monitoring period will be 28 days starting Day 15 of Cycle 1. Subjects withdrawing from investigational treatment during the 28 day DLT monitoring period for a reason that is definitely unrelated to toxicity of the study agent (e.g. disease progression, patient withdrawal of consent) will be replaced for the safety analysis. 3-6 patients will be enrolled at in Stage 1 as determined by 3+3 rules. These patients will also be evaluated for efficacy.

Stage 2

Stage 2 of the study will include an expansion cohort of up to 21 additional subjects for a total of 24 subjects to evaluate the efficacy of the combination of blinatumomab and pembrolizumab. All patients receiving combination therapy starting day 15 of cycle 1 will be considered evaluable for overall response rate of entire population, RFS and OS.

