10.5 Data Analyses Plans

10.5.1 Primary Analysis

Simon's 2-stage for efficacy

We plan a Simon's 2-stage MiniMax design evaluation of the combination of blinatumomab and pembrolizumab in relapsed or refractory B-cell ALL with >50% blasts in the marrow.

We assessed the sample size for studying using overall response rate (CR + CRh). From recent large Phase II study including 189 subjects with relapsed/refractory B-lineage ALL, ORR (CR + CRh) to blinatumomab monotherapy was approximately 29% in patients with >50% lymphoblasts in the bone marrow (Topp et al. 2015). Response rates for PD-1 inhibitors in relapsed or refractory ALL are unknown but given mechanism of action it likely approaches zero.

An absolute increase in the overall response rate of 25 percentage points (i.e. to 54% ORR in patients evaluable for efficacy) or greater will demonstrate sufficient activity to consider the regimen for further study.

To calculate sample sizes for Stage 1 and Stage 2 we used a probability of type I error (α) = 0.05 and a power ($1-\beta$) = 0.80 with $p_0=0.29$ and $p_1=0.54$.

The null hypothesis that the true response rate is 0.29 will be tested against a one-sided alternative. In the first stage, 18 patients evaluable for efficacy will be accrued. If there are 7 or fewer responses in these 18 patients, the study will be stopped. Otherwise, 6 additional patients will be accrued for a total of 24 patients evaluable for efficacy of the combination. The null hypothesis will be rejected if 11 or more responses are observed in 24 evaluable patients. This design yields a type I error rate of 0.05 and power of 0.80 when the true response rate is 0.54. The likelihood of early termination is 0.88, if the null hypothesis is true.

Safety rules

At the time of the Stage 1 efficacy analysis, all patients will be reviewed again for DLTs as defined in Section 5.1.4 occurring at any time during therapy.

A DLT rate exceeding 0.3 will be considered unacceptable. The first 3, 6, 12, and 24 patients will be monitored for DLTs. The first 6 patients will be monitored every other week. The next 6 patients will be monitored monthly. Subsequent patients will be monitored every other month.

k	1	2	3	4
n_k	3	3	6	12

N_k	3	6	12	24
r_k	1	1	3	5

Table: Monitoring design for DLTs. The stage is denoted by k . The number of patients accrued during and up to stage k are denoted by n_k and N_k respectively. The critical value at stage k is denoted by r_k .

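### Sections 10.4 and 7.1.1 define the primary ORR denominator differently, and 10.5.1 does not say which one its 18- and 24-patient rules use

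*Combined protocol and SAP*

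**What the plan says.** Two sections define who counts for response.

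- Section 10.4 (Stage 2): "All patients receiving combination therapy starting day 15 of cycle 1 will be considered evaluable for overall response rate". It names RFS and OS as well. Under Stage 1 it adds that the safety run-in patients are also evaluated for efficacy.
- Section 7.1.1: only patients with measurable disease at baseline "who have received at least one cycle of therapy and have had their disease re-evaluated will be considered evaluable for response".

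Section 10.5.1 builds the primary test on evaluable patients: "In the first stage, 18 patients evaluable for efficacy will be accrued", and "The null hypothesis will be rejected if 11 or more responses are observed in 24 evaluable patients". The target is on the same footing ("i.e. to 54% ORR in patients evaluable for efficacy"). The section neither defines the term nor refers to 10.4 or 7.1.1.

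Other relevant text:

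- Section 3.1 sets the endpoint as response "after 1 or 2 cycles of combination therapy".
- Section 5.1.3 gives a 28-day blinatumomab infusion in a 42-day cycle, and says that patients without CR/CRh after two cycles or "progressing after Day 15 of Cycle 1 will go off study".
- Section 5.1.6 schedules marrows at "Cycle 1, Day 12, 13, or 14" and again from Day 29.
- Sections 5.1.1, 5.1.4 and 10.4 replace Stage 1 patients who leave during the DLT period for reasons unrelated to toxicity, disease progression included.
- Section 5.1.5 enrols 24 in total, whereas 10.5.1 requires 24 evaluable.

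**The concern.** The two definitions part company for one kind of patient: someone who receives pembrolizumab on Cycle 1 Day 15 and then progresses, dies or withdraws before completing a cycle. Under 10.4 that patient is in the denominator and adds no response. Under 7.1.1 the patient is left out. The Day 12–14 marrow might satisfy the re-evaluation condition, but not the one-cycle condition.

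Such patients are early failures, so leaving them out raises the response rate in the analysed set. In a single-arm, open-label trial, the choice of denominator should not remain open once outcomes are known. The replacement text does not close the gap: it concerns DLT evaluability and does not say whether a replaced patient stays in the efficacy set. If early failures were dropped, the stated 0.05 would no longer be assured and the futility stop would be less likely to work when the combination adds nothing.

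**Working it through.** **Inputs (10.5.1).** p0 = 0.29, p1 = 0.54; n1 = 18, stop if 7 or fewer responses; n = 24, reject if 11 or more. Stated: type I error 0.05, power 0.80, early termination under the null 0.88.

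**Step 1: reproduce the plan's figures.** With X1 the responses in the first 18 and X2 those in the next 6:

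- Early termination = P(X1 ≤ 7 | 18, p)
- Rejection = sum over x = 8 to 18 of P(X1 = x | 18, p) × P(X2 ≥ 11 − x | 6, p)

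At p = 0.29:

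| x | P(X1 = x) | P(X2 ≥ 11 − x) | Product |
|---|---|---|---|
| 8 | 0.0713 | 0.2374 | 0.0169 |
| 9 | 0.0323 | 0.5580 | 0.0180 |
| 10 | 0.0119 | 0.8719 | 0.0104 |
| 11 or more | 0.0046 | 1 | 0.0046 |

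The sum is 0.0499. Early termination is 0.880, and power at p = 0.54 is 0.801. The plan's figures are right, and the margin below 0.05 is 0.0001.

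**Step 2: who is affected.** For a patient who starts the combination on Day 15:

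| Leaves treatment | Section 10.4 | Section 7.1.1 |
|---|---|---|
| Before the infusion ends on Day 28 | In, no response | Out |
| Around the Day 29 marrow | In | Unclear: in if one cycle means the 28-day infusion, out if it means 42 days |
| After a full cycle with a re-evaluation | In | In |

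**Step 3: dropped and replaced.** Assume that 0.29 is the null rate in the 10.4 set, and that k non-responders are dropped for every 24 patients retained. The null rate in the retained set is 0.29 × (24 + k)/24.

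- k = 1: 0.29 × 25/24 = 0.302; type I error 0.065; early termination 0.855.
- k = 2: 0.29 × 26/24 = 0.314; type I error 0.084; early termination 0.827.

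**Step 4: dropped, not replaced.** Fix 24 patients in the 10.4 set, drop k non-responders, keep the cut-off at 11, and take the interim at the 18th retained patient. Let R be the responders among the 24, and H the number of responders among 18 drawn from the 24 − k retained.

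- Type I error = sum over R ≥ 11 of P(R | 24, 0.29) × P(H ≥ 8)
- k = 1: 0.055. k = 2: 0.058.
- Ceiling: success always needs 11 responders, so it cannot exceed P(R ≥ 11 | 24, 0.29) = 0.060.

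Dropping non-responders does not change the count of responders. Without replacement, therefore, the verdict can differ only because the interim falls on different patients. Example: 7 of the first 18 patients in the 10.4 set respond, one of the 11 non-responders is dropped under 7.1.1, and the 19th patient responds. Section 10.4 stops at 7/18; Section 7.1.1 continues at 8/18.

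**Step 5: power, if 0.54 was meant for the 7.1.1 set.** The rate in the 10.4 set would be 0.54 × 24/(24 + k).

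- k = 1: 0.54 × 24/25 = 0.518; power 0.739.
- k = 2: 0.54 × 24/26 = 0.498; power 0.674.

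**The case against.** The best defence is that 10.4 plainly governs. It sits in the statistics chapter just before 10.5.1, its title concerns evaluable subjects, and it names the overall response rate. Section 7.1.1 is a general definition tied to no analysis. That makes 10.4 the likelier intention. It does not remove the conflict: 7.1.1 is worded as exclusive, it stands in the same Section 7.1 that defines ORR, and nothing says that 10.4 overrides it.

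Several further objections stand and limit the point.

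- The larger figures need four things at once: 7.1.1 is followed, losses are replaced, the dropped patients are non-responders, and 0.29 applies to the 10.4 set. Without replacement the effect is small.
- A reader might infer that replacement is confined to the safety analysis. That phrase is in 10.4, but 5.1.1 and 5.1.4 state replacement without it. All three concern Stage 1 DLT evaluability and are silent on the efficacy set.
- A reader might infer that 10.2 also contradicts 10.5.1 on the 24. It does not: it gives an accrual goal and refers to 10.5.1 for the reason. The mismatch is with 5.1.5.
- The lack of an explicit non-responder rule does not make a 10.4 analysis ambiguous. CR and CRh have positive criteria in 7.1.4.1, so a patient without them adds no response. Stating the rule is good practice.
- Adopting 10.4 does not settle everything. It leaves out losses on Days 1–14, and the documents do not give the denominator behind the 29%.

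**Conclusion.** The conflict is in the current text and concerns the denominator of the primary test, so it should be fixed. Confidence is high on the wording and lower on the consequences. Under the assumptions in Steps 3 and 4, one or two dropped early failures move the type I error from 0.0499 to 0.065 or 0.084 if they are replaced, and to 0.055 or 0.058 (never above 0.060) if they are not. With replacement, early termination under the null falls from 0.880 to 0.855 or 0.827. The documents give no early-failure rate, so these are illustrations.

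Three stronger readings are not supported. The two-stage design is not miscalculated: its figures reproduce. The trial's type I error cannot be said to exceed 0.05, because under 10.4 it stays at 0.0499 if 0.29 is the null rate in that set. Nor can the two definitions give opposite final verdicts on the same patients at will: without replacement, only the interim look can do that.

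**What to change.** **Required by the contradiction**

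- In 10.5.1, define the patients evaluable for efficacy as the 10.4 set: all who receive the combination from Cycle 1 Day 15. Amend 7.1.1 to match for the ORR analysis.
- Count any patient in that set without a documented CR/CRh by the end-of-Cycle-2 assessment as a non-responder, whatever the reason.
- State that patients replaced for DLT evaluation stay in the efficacy set.
- Apply the interim and final rules to the first 18 and first 24 patients in that set, and align the 24 in 5.1.5 with 10.5.1.

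**Optional**

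- State the denominator behind the 29%.
- Report a sensitivity ORR in all patients who start blinatumomab, because the 10.4 set leaves out losses on Days 1–14.

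**Cost.** These are mainly text edits. The observed ORR may be slightly lower than under 7.1.1. If 0.54 was meant for the 7.1.1 set, power in the 10.4 set is 0.74 with one such loss per 25 patients, or 0.67 with two per 26, against the planned 0.80. The sponsor should therefore say which set the 0.54 refers to. If patients are lost before Day 15, reaching 24 in the set takes more than 24 enrolled, as the wording of 10.5.1 already implies.

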A Phase 2, single-arm, multi-center study, blinatumomab was given at 9 µg/day for the first 7 days and 28 µg/day thereafter by continuous intravenous infusion over 4 weeks every 6 weeks for up to five cycles to 189 subjects with relapsed or refractory B-lineage ALL. Blinatumomab monotherapy yielded an overall response rate (CR + CRh) of 43% with all responses occurring within 2 cycles of therapy (Topp et al. 2015). However, blinatumomab achieves CR/CRh rates of only 29% in B-ALL patients with ≥50% lymphoblasts in the bone marrow versus 73% in subjects with <50% lymphoblasts in the bone marrow. Median overall survival was 6.7 months for all patients and 3.1 months for patient not achieving a CR/CRh [8].

Blinatumomab is generally well tolerated. Reversible neurotoxicity including confusion, aphasia, paresis, and seizures may occur with blinatumomab. A potentially serious but rare toxicity of blinatumomab is a cytokine release syndrome (CRS) characterized by fever, hypotension, and occasionally pulmonary toxicity leading to acute respiratory distress syndrome. The incidence of Grade ≥3 CRS in 211 patients studied was 1.3%. The physiologic consequences of the cytokine release syndrome are associated with elevated levels of proinflammatory cytokines including IFN-gamma, TNF-alpha, IL-10, IL-6, and IL-2 [9]. The syndrome is associated with high disease burden and can be ameliorated with corticosteroids or the anti-IL6 antibody tocilizumab [10].

The relatively high overall response rate with blinatumomab monotherapy led to FDA approval of the drug in 2015 and it is now a standard treatment option for relapsed or refractory B-cell ALL. Despite its impressive activity in patients with MRD+ and low bone marrow blast count ALL, response rates of approximately 30% in patients with bone marrow blasts counts greater than 50% parallel those seen with multiagent chemotherapy. The reasons for this disparity in response are unclear and insufficient T-cell activation by blinatumomab or suboptimal dosing of blinatumomab may be potential mechanisms.

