3.2 Secondary Endpoints

3.2.1 CR rate as defined above.

3.2.2 Minimal residual disease (MRD) negativity in subjects achieving a CR or CRh will be defined as less than 0.01% residual lymphoblasts by multiparameter flow cytometry.

3.2.3 2-year relapse-free survival (RFS) will be defined as the time from achieving CR or CRh to relapse defined as the reappearance of lymphoblasts in bone marrow or blood at >5% of cells or reappearance of extramedullary disease.

3.2.4 2-year overall survival (OS) will be defined as the time from starting study therapy to death from any cause.

3.2.5 ORR, CR rate, 2-year RFS, and 2-year OS in the Ph/BCR-ABL1-negative and Ph/BCR-ABL1-positive populations separately.

3.2.6 Allogeneic hematopoietic cell transplantation (HCT) rate in transplant-eligible subjects will be defined as the number of patients eligible for allogeneic HCT as determined by the investigator who actually proceed to transplant.

3.2.7 Safety and tolerability of blinatumomab in combination with pembrolizumab will be defined by treatment-emergent Grade 2-5 adverse events (AEs) defined using NCI CTCAE v4.03 toxicity criteria attributable to study therapy.

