6.2 Procedures During Treatment

Lumbar puncture with intrathecal methotrexate 15 mg day 29 + 8 days during cycles 1-4 and day 38 + 8 of cycle 5 for total of 6 doses including dose given at screening. CSF studies with each lumbar puncture: Cell count with differential, cytology, and flow cytometry.

Adverse events and concomitant medications to be collected continuously while on study.

Cycle 1

Day 1

Collection of Serum Cytokine Assay samples (See **Section 6.5**) prior to blinatumomab

Administration of Blinatumomab 9 mcg/d CIV on days 1-7 (hospital admission required per section 5.1.3)

Physical exam, performance status, vital signs, weight

Vital signs (heart rate and oxygen saturation) to be monitored continuously and full vital signs (temperature, heart rate, blood pressure, respiratory rate, and oxygen saturation) every 4 hours during at least the initial 72 hours of blinatumomab therapy, for 72 hours after all restart or step-up doses, and for at least the initial 72 hours following the first (Cycle 1, Day 15).

Labs: CBC with differential, CMP (sodium, potassium, chloride, bicarbonate, BUN, creatinine, glucose, calcium, total bilirubin, AST, ALT, alkaline phosphatase), direct bilirubin

Adverse Event Assessment

Concomitant Medications

Day 2

Collection of Serum Cytokine Assay Samples 24 hours +/- 2 hour after start of blinatumomab (See **Section 6.5**)

Day 3

Collection of Serum Cytokine Assay samples 48 hours +/- 2 hours after start of blinatumomab (See **Section 6.5**)

Day 8

Collection of Serum Cytokine Assay samples (See **Section 6.5**) prior to increase in blinatumomab dose

Start administration of Blinatumomab 28 mcg/d CIV days 8-28

Day 9

Collection of Serum Cytokine Assay Samples 24 hours +/- 2 hour after start of blinatumomab 28 mcg/day (See **Section 6.5**)

Day 10

Collection of Serum Cytokine Assay samples 48 hours +/- 2 hours after start of blinatumomab 28 mcg/day (See **Section 6.5**)

Day 14

Labs: CBC with differential, CMP (sodium, potassium, chloride, bicarbonate, BUN, creatinine, glucose, calcium, total bilirubin, AST, ALT, alkaline phosphatase), direct bilirubin, amylase and lipase

Procedures: Bone marrow aspiration and biopsy. Send for standard histology, flow cytometry, cytogenetics (karyotype and *in situ* hybridization for previously documented abnormalities required, other testing per institutional standard of care) and quantitative PCR for BCR-ABL1 p190 and/or p210 if previously positive.

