7.1.7 Overall Survival

Overall survival is defined as the duration of time from start of treatment to death from any cause.

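### ORR and OS count only patients who start the combination on Cycle 1 Day 15, while OS is timed from Day 1 and the 29% benchmark carries no stated Day-15 condition; any resulting bias favours the regimen

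*Combined protocol and SAP*

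**What the plan says.** - **Efficacy set.** Section 10.4 (Stage 2): "All patients receiving combination therapy starting day 15 of cycle 1 will be considered evaluable" for ORR in the whole population, RFS and OS. Section 10.5.1 counts its 18 and 24 patients as evaluable for efficacy. No efficacy analysis of all treated patients is specified.
- **OS clock.** Section 3.2.4 says OS "will be defined as the time from starting study therapy to death from any cause". Section 7.1.7 agrees: "Overall survival is defined as the duration of time from start of treatment to death from any cause".
- **Start of therapy.** Section 6.2 lists under Cycle 1 Day 1: "Administration of Blinatumomab 9 mcg/d CIV on days 1-7". The first pembrolizumab dose is on Day 15.
- **A second response set.** Section 7.1.1 requires measurable disease at baseline and limits response to patients "who have received at least one cycle of therapy and have had their disease re-evaluated will be considered evaluable for response".
- **Benchmark.** Sections 1.2.1 and 10.5.1 give about 29% for blinatumomab monotherapy in the high-blast subgroup of a 189-subject study. Neither section says how the subgroup's denominator was formed or mentions a Day-15 condition.
- **Decision rule (10.5.1).** p0 = 0.29, p1 = 0.54. Stop at 7 or fewer responses in 18; reject the null at 11 or more in 24. Stated type I error 0.05, power 0.80, early termination probability under the null 0.88.

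**The concern.** Entry to the OS set requires surviving to Day 15, but those 14 days are counted as survival time. This is immortal time, and it can only raise the Kaplan-Meier curve.

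The same rule removes from the ORR denominator anyone who starts blinatumomab but does not reach the combination. If the 29% rate was computed over all treated patients, the trial compares a selected group with an unselected one, and the primary decision loses its stated error rate.

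Section 7.1.1 selects further. A patient who receives pembrolizumab on Day 15 and dies on Day 20 is a non-responder under 10.4 but is excluded under 7.1.1. With cut-offs of 8 in 18 to continue and 11 in 24 to reject, the classification of one patient can change the outcome. That conflict needs no assumption about loss rates.

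**Working it through.** **1. The plan's own figures.** With X1 responses in the first 18 patients and X2 in the next 6:

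- Early termination = P(X1 ≤ 7 | 18, p)
- Rejection = Σ over x = 8 to 18 of P(X1 = x) × P(X2 ≥ 11 − x | 6, p)

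At p = 0.29, early termination is 0.880 and rejection 0.0499. At p = 0.54, rejection is 0.801. The stated 0.88, 0.05 and 0.80 are reproduced, and a search confirms that this is the minimax design. The design arithmetic is sound; the question is which patients it is applied to.

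**2. Effect of the Day-15 restriction on the test.** Let d be the share of treated patients lost before Day 15. Assume that none of them responds, and that 29% is a rate among all treated patients. A regimen no better than the benchmark then shows a rate of 0.29/(1 − d) in the Day-15 set. The same rule at that rate gives:

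| d | Null rate in Day-15 set | Type I error | Early termination |
|---|---|---|---|
| 0% | 0.2900 | 0.050 | 0.88 |
| 1.3% | 0.2938 | 0.054 | 0.87 |
| 4% | 0.3021 | 0.065 | 0.85 |
| 5% | 0.3053 | 0.070 | 0.85 |
| 10% | 0.3222 | 0.098 | 0.81 |
| 15% | 0.3412 | 0.137 | 0.75 |
| 20% | 0.3625 | 0.191 | 0.69 |

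The documents do not give d. The value 1.3% borrows the Grade ≥3 cytokine release frequency in Section 1.2.1 (211 patients) as a low illustration; it is not an early-loss rate. The value 4% is one loss in 25 treated. The remaining values are assumed. The type I error reaches 0.10 at d of about 10.4%.

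**3. OS.** Let S be the 2-year OS in the Day-15 set. OS among all treated patients is at least S(1 − d), so the overstatement is at most S × d, reached only if no lost patient survives 2 years. For assumed S of 15% to 35% and d of 5% to 20%, the bound runs from 0.15 × 0.05 = 0.75 points to 0.35 × 0.20 = 7 points.

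**4. The rule applied to all treated patients.** With early exits as non-responders, the type I error at 0.29 is 0.0499. Power is 0.80 if 54% is the target among all treated patients. Section 10.5.1 sets 54% for evaluable patients. If that meaning is kept, the all-treated rate is 0.54(1 − d): 0.513 at d = 5% (power 0.72) and 0.486 at d = 10% (power 0.63).

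**The case against.** The strongest defence is that the restriction is deliberate. Section 3.1.1 defines response after combination therapy, 10.5.1 sets the target among evaluable patients, and pembrolizumab cannot act before Day 15. This justifies a Day-15 population. It does not justify timing that population's OS from Day 1, or testing it against a rate not known to carry the same condition.

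Several limits on the concern do stand:

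- **Progression.** A reader might infer that all early failures drop out. Sections 5.1.3 and 5.8 end treatment for progression only after Day 15. A patient who progresses on Day 10 and receives pembrolizumab on Day 15 stays in the 10.4 set.
- **Toxicity.** Cytokine release or neurotoxicity is not the same as exit. In the blinatumomab columns of Section 5.7.1, Grade 1–2 events generally continue and Grade 3 events are generally withheld and resumed; Grade 4 events and specified others end protocol therapy. For Grade 3 cytokine release, the pembrolizumab column ends trial treatment while the blinatumomab column resumes it. Those entries must be reconciled.
- **Benchmark.** A reader might take 29% as the rate over all 189 subjects. Section 1.2.1 attaches another figure to that population: "Blinatumomab monotherapy yielded an overall response rate (CR + CRh) of 43" per cent. The 29% is the high-blast subgroup rate. That it carries no Day-15 condition is the natural reading, since monotherapy has no combination start, but its denominator should be confirmed.
- **OS.** It is a secondary, descriptive estimate (10.5.2), with no test and no benchmark.

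**Conclusion.** The concern holds in a limited form. The Day-15 entry rule, the Day-1 OS clock, the absence of an all-treated efficacy analysis and the conflict between 7.1.1 and 10.4 are all in the text. Any bias favours the regimen.

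The size is conditional. If 29% applies to all treated patients and no lost patient responds, the type I error rises from 0.050 with no loss to 0.070 at 5%, 0.098 at 10% and 0.191 at 20%. A reader might conclude that the trial's error rate is in fact near 0.19. The documents do not support that, because they give no early-loss rate, and with no loss there is no bias. For OS, S × d is an upper bound, since patients who withdrew or stopped for toxicity may survive 2 years. The effect on ORR matters more than the effect on OS, because only ORR drives a decision.

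**What to change.** 1. **OS.** Estimate it from Day 1 in all patients who start blinatumomab. If a Day-15 curve is also shown, start its clock at Day 15.
2. **ORR.** Report it in all patients who start blinatumomab, with early exits as non-responders. A table beside the Simon decision does not change that decision's error rate, so also do one of the following:
   - apply the 7/18 and 11/24 rule to the all-treated set (type I error 0.0499, N still 24, power 0.80 if 54% is restated as an all-treated target); or
   - keep the Day-15 set for the decision, and state that 0.05 holds only if the 29% benchmark applies to patients who reach Day 15.
3. **Section 7.1.1.** Delete its response-evaluable definition or align it with 10.4, so that patients without re-evaluation count as non-responders.
4. **Benchmark.** Confirm and state the denominator behind 29%.

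Section 7.2 already uses an all-treated set for safety, so no new data are needed. The cost is revised analysis wording and added output. ORR and OS may be slightly less favourable, and the first option under item 2 has less power if 54% continues to mean the rate among patients who reach Day 15.
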